#### **IV. SUBJECT ENROLLMENT**

This is a nation-wide proof-of-concept randomized controlled trial conducted entirely remotely. We will enroll 225 nondaily smokers based on the following eligibility criteria: (a) 18+ years of age, (b) smartphone ownership (Android or iPhone only) (c) current nondaily smoker, who smokes at least weekly, and no more than 25 out of the past 30 days, and (d) lifetime history of having smoked 100+ cigarettes, and (e) is willing to make a smoking quit attempt as part of this study.

Participants will participate in screening, consisting of (1) a phone screen, (2) an online screening survey, which will contain check-questions to verify that respondents are truly reading items (100% accuracy required; If less than 100% accuracy, participant is screened out unless there is a compelling reason to justify missed check items. This would only happen upon review with the PI and after a phone conversation with the study participant has taken place to review the missed item(s) and explain the situation. Examples would include survey glitch, otherwise thoughtful write-in answer indicating survey attention, careful review of other survey answers and length of time spent on survey); (3) provision of contact information for two collaterals who can assist research staff in locating participants; collaterals will be told that the participant is participating in a study tracking health behaviors; and (4) provision of their social security number to enable remuneration by check, as required by MGH. We expect that 1/3 of participants who start the online survey will enroll in the study.

During the phone screen, research staff will provide an overview of the study, and will answer any questions participants may have about the study. If found eligible during the phone-screen (see attached phone screen script), staff will email a pdf of the study fact sheet to the potential participant, using SEND SECURE or not, based on the potential participant's preference, as indicated during the phone screen. The study fact sheet provides an outline of the nature of the study, risks and benefits to participation, details on remuneration for participation, and how to contact with PI or IRB staff in case they have any concerns (see attached study fact sheet). The same email will contain a person-specific link to the online survey and a general resource sheet. Participants are encouraged to ask questions about the study and anything they have read in the study fact sheet prior to clicking on the survey link. When the participant starts the survey, they will be presented with the same study fact sheet in REDCap that they have received via email. They must click "I agree to participate in this screening survey" in order to proceed to the survey. The study fact sheet reminds participants that, at this point, they are agreeing to participating in the online survey: "Once we have reviewed your survey responses, we will contact you to proceed with the remaining parts of the screening test. If you are eligible to enroll in this study, and you decide you would like to participate in this study, we will ask you for your verbal consent to participate in the study during a phone call with study staff."

Staff will receive an automatic email from REDCap once the screening participant has completed the survey. If the screening participant incorrectly responded to the check items

(please see attached for the specific check items), staff will inform the screening participant that they are ineligible for the study. If the survey is complete and valid, staff will collect (via email, phone, and/or REDCap form) the contact information for collaterals the participant would like to specify for this study. Social security number (to enable payment by check) and a mailing address to which Accounts Payable can mail the check containing remuneration will be collected via phone, and only after participants have been enrolled in the study. For screen participants who do not enroll in the study (i.e., because they are ineligible or because they decide against the study) study staff will ask for verbal consent (via phone) to allow us to collect their SSN (during the same phone call) and send them a check for completing the screening survey.

At the end of this phone call, study staff will ask the screening participant to indicate the date on which they would like to quit smoking. The enrollment call is then scheduled to occur 8 days before that date. If the chosen quit date falls on a Monday or Sunday, meaning that the enrollment call should be on a Saturday or a Sunday, the enrollment call will be adjusted to fall on a weekday.

During the enrollment call, staff will review the study fact sheet with the participant, and will invite the participant to ask any questions they may have about the study and all its procedures. Once all questions have been answered, study staff will ask the participant to give verbal consent to enroll in this study. The date and time of this verbal consent will be documented by study staff in our REDCap dataset.

After providing verbal consent, the participant is randomized. This is an unblinded study. Randomization will occur via a randomization sheet, as generated using the PROC PLAN procedure in the statistical software package SAS. Randomization will be in a 1:1:1 ratio (SiS3 vs. QG vs. TAU), with a block size of 4. Study staff will use the randomization sheet to determine the participant's treatment group, document this randomized assignment in our REDCap dataset, and will then onboard the participant to the smoking cessation support they have been randomized to receive (i.e., our smartphone app SiS or NCI's app QuitGuide or TAU, which consists of NCI's written materials, "Clearing the Air"), using a time-matched, ~15 minute script.

We will stop enrollment when n=225 participants have been successfully onboarded to their randomized condition. Based on our experience in Study 1 (#2017P001106) and Study 2 (#2018P002699), we expect that 1/3 of participants who start the screening survey will enroll in the study. Thus, we are estimating that n=675 will be necessary to start the screening survey in order for n=225 to be successfully enrolled to their randomized treatment condition.

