## II. SPECIFIC AIMS

This is the third study in a series of 3 studies to develop a smartphone app to support nondaily smokers in quitting smoking, as funded by the American Cancer Society grant #RSG CPPB – 130323 (project dates: 07/01/2017 – 6/30/2021). Study 1 (2017P001106) demonstrated feasibility and acceptability when smokers were onboarded in person. Study 2 (2018P002699) demonstrated feasibility and acceptability when smokers were onboarded remotely, nationwide. The present study is Study 3. It is a 3-group proof-of-concept RCT, in which we seek to test if our app (i.e., Version 3 of our developed smartphone app, called ‘Smiling instead of Smoking’ (SiS)) is superior to treatment as usual (i.e., TAU; no treatment for nondaily smokers) and superior to a control app (i.e., the National Cancer Institute’s smartphone app “QuitGuide” (QG). Specifically, our aims are to:

1. Test for differences between randomized groups on the primary outcome of this proof-of-concept RCT, as measured at end of treatment (i.e., Week 6 post-quit): Self-efficacy to remain abstinent, as measured via the Smoking Self-Efficacy Questionnaire (SEQ): two-dimensional 12-item self-report scale measuring a person’s confidence in his or her ability to abstain from smoking when facing internal stimuli [e.g. feeling depressed] and external stimuli [e.g. being with smokers]. Participants rate each item on a sliding scale from 0 [not at all confident] to 100 [extremely confident]. Two subscale scores are created by averaging items assessing internal vs. external stimuli, respectively. We hypothesize that SiS > QG > TAU.
2. Test for differences between randomized groups on secondary outcomes:
  - a. Self-reported 30-day point-prevalence abstinence 6, 12 and 24 weeks post quit. We hypothesize that SiS > QG > TAU.
  - b. Self-reported past week cigarette reduction at 2, 6, 12, and 24 weeks post quit, compared to baseline. We hypothesize that SiS > QG > TAU.
  - c. Satisfaction with smoking cessation support, as self-rated on the Client Satisfaction Questionnaire (CSQ-8) at end of treatment. We hypothesize that SiS > QG > TAU.
  - d. Time spent applying content brought up by the apps/”Clearing the Air” at end of treatment (“During this past week, how much time did you spend applying or contemplating the content of the SiS app/QG app/”Clearing the Air”?” [in minutes]). We hypothesize that SiS > QG > TAU.

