## VI. BIOSTATISTICAL ANALYSIS

**Statistical Power.** This is a proof-of-concept trial. Therefore, our primary endpoint is a process variable, a shorter-term variable that is linked to subsequent change on the outcome of ultimate interest. In this case, ultimately, the SiS app is hoped to have an effect on smoking cessation 6 months after the chosen quit day. Typically, effect sizes for mHealth interventions for smoking cessation are very small; their public health importance lies in their potential reach, where a small effect in a large population can make a considerable impact on public health. Specifically, for interventions delivered via websites, meta-analyses have reported an overall odds ratio for point prevalence abstinence of 1.14 [1.07-1.22], and Cohen's d=0.12. For text messaging, a Cochrane review estimated a relative risk of 1.54 [1.19-2.00] in favor of automated text messaging interventions compared to minimal smoking cessation support. Such effect sizes require large scale RCTs, which is beyond the scope of this proof-of-concept RCT. Thus, as a process indicator of subsequent smoking cessation, we have selected self-efficacy to abstain from smoking as our primary outcome variable, because self-efficacy has been identified as the primary mediator by which a text-messaging intervention conferred smoking cessation benefit. Similar to our study, this trial used the "Clearing the Air" booklet as the control condition, and

showed that self-efficacy observed one month after the chosen quit day mediated group differences in smoking cessation at the 6-month follow-up.

In selecting the sample size for this proof-of-concept trial, we were guided by the effect observed in that text-messaging trial. Namely, in the text-messaging study, the observed group difference between treatment and control at 1 month post quit day on self-efficacy was  $d=0.66$ . Thus, we conservatively powered our proof-of-concept RCT to detect an effect size of  $d=0.50$ . Using SAS PROC POWER, we calculated that we would need a sample size of  $n=64$  per group to detect an effect of  $d\geq0.50$ . Assuming a retention rate of 85%, we would need to enroll  $n=75$  per group in order to retain  $n=64$  by end of treatment. Thus, the total number of participants to be enrolled into this trial is  $n=225$  (3 randomized groups \* 75 participants to be enrolled in each group = 225).

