**Analytic Plan.** All successfully enrolled participants (i.e., passed the screening process, was successfully onboarded to the assigned smoking cessation materials) will be included in the outcome analyses. For hypotheses only relevant to the SiS and QG conditions (marked in Specific Aims), only participants successfully onboarded to those conditions will be included in the analyses.

1. **Primary Outcome (Aim 1).** In this proof-of-concept RCT, the primary outcome is self-efficacy to abstain from smoking, as measured by the SEQ-12. The primary endpoint is end-of-treatment, which occurs 6 weeks after the originally chosen quit day. To test for differences between randomized groups, we will fit a fixed effects repeated measures model using PROC MIXED, where observations are modeled as nested within persons. Predictors included in the model will be GROUP (i.e., SiS vs. QG vs. TAU), TIME (i.e., BL, Week 2, Week 6, Week 12 and Week 24), and the GROUP\*TIME interaction effect. A contrast statement will be used to derive the test statistic for the GROUP comparison at Week 6, our primary endpoint, given the overall longitudinal model. This contrast statement will test the null hypothesis that SiS = QG = TAU. If this null hypothesis is rejected ( $p<0.05$ ), we will conduct pair-wise follow-up tests that compare the three possible pairwise comparisons (i.e., SiS vs. QG, SiS vs. TAU, and QG vs. TAU).
2. **Secondary Outcomes (Aim 2).** The secondary outcomes in this proof-of-concept RCT are exploratory. Thus, we will not correct for multiple testing. We will fit one model per secondary outcome, using an alpha of 0.05 for all analyses.
  - 2.1. To test for differences between randomized groups for outcomes that are assessed multiple times (Aims 2a, 2b), our overall modeling approach will be the same as for Aim 1. That is, for each outcome, we will fit a fixed effects repeated measures model, where observations are modeled as nested within persons. Predictors included in the model will be GROUP, TIME, and the GROUP\*TIME interaction effect. However, for these secondary outcomes, the definitions of the TIME effect varies across these secondary outcomes, based on their assessment schedule. The distribution of the outcome variables also varies across these variables. Thus, we will implement this overall modeling approach for these variables as follows:

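### The stated block size of 4 does not fit 1:1:1 randomisation to three arms

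*Combined protocol and SAP*

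**What the plan says.** Section IV describes the allocation in a few sentences. Participants are allocated once they have consented on the enrolment call ("After providing verbal consent, the participant is randomized"). The source is a prepared list: "Randomization will occur via a randomization sheet, as generated using the PROC PLAN procedure in the statistical software package SAS". The ratio and blocking follow: "Randomization will be in a 1:1:1 ratio (SiS3 vs. QG vs. TAU), with a block size of 4". Enrolment ends on a count of people onboarded, not of people randomised: "We will stop enrollment when n=225 participants have been successfully onboarded to their randomized condition".

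The number of arms is not in doubt. Section II (Specific Aims) says "It is a 3-group proof-of-concept RCT", and the power paragraph of section VI (Biostatistical Analysis) arrives at "75 participants to be enrolled in each group = 225".

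Block size is mentioned nowhere else. The document does not say that 4 means four per arm, that a doubled arm rotates or is drawn at random, or that block lengths vary. The stratified enrolment by sex and by race and ethnicity in section III (Subject Selection) concerns who is recruited and does not account for a block of 4.

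**The concern.** Blocking is used to keep the arms close to the intended ratio throughout enrolment. With three equal arms, each block must hold the same number from each arm, so its length must be a multiple of 3. A block of 4 containing all three arms has two participants from one arm and one from each of the others. Which arm is doubled, and by what rule, is not stated.

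The rules one might guess give different protection against imbalance. The reader therefore cannot tell from the text what balance the blocking guarantees, or check the stated structure against the stated ratio. The sentence is complete, with no redaction or gap, so the conflict is not an artefact of how the text was extracted.

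**Working it through.** **Inputs.** Three arms, ratio 1:1:1 and block size 4 (section IV); 225 enrolled, 75 per arm, d = 0.50 and 85% retention (section VI). Assumed, because the power paragraph states neither: two-sided alpha 0.05 and 80% target power, with a two-sample t-test.

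**1. The plan's sample size.** The t-test with 64 per group has power 0.801 at d = 0.50, so the stated 64 is reproduced. 64/0.85 = 75.3 against the stated 75; 75 × 0.85 = 63.75 retained, with power 0.800. 3 × 75 = 225. None of this uses the block size.

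**2. Divisibility.** 4/3 = 1.33 per arm, which is not whole, and 225/4 = 56.25 blocks. By contrast, 225/3 = 75 and 225/9 = 25 complete blocks. Lengths 6 (37.5 blocks) and 12 (18.75 blocks) are valid but end on a part block.

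**3. Arm sizes at 225 under the possible readings, with no loss before onboarding.**
- *Same arm doubled every time:* 56 blocks give 112:56:56, plus one participant. This contradicts both 1:1:1 and 75 per group, so it is set aside.
- *Doubled arm rotates:* balance returns every 12 rows. 18 cycles = 216 rows, or 72 per arm. Two more blocks (8 rows) add 3:3:2 and one further row completes 225, giving 75:75:75 or 76:75:74. Gap at most 2.
- *4 means four per arm (length 12):* 18 blocks = 216 rows. Nine rows of the next block add at worst 4:4:1, giving 76:76:73. Gap at most 3.
- *Doubled arm random:* each arm gets 56 plus its share of 56 random extra slots, plus one final row. Simulation gives a median gap of 7, a 95th percentile of 14, and a gap above 3 in about 83% of lists.
- *No blocking, for comparison:* median 14, 95th percentile 29.

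**4. Loss between randomisation and onboarding.** Participants are randomised first and counted only when onboarded, so the limits of 2 and 3 hold only if nobody drops out in between. The document gives no loss rate. Assuming random loss, the gap among the first 225 onboarded is:

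| Assumed loss | Rotated slot, or length 3, 6 or 12: median, 95th percentile | Random slot: median, 95th percentile |
|---|---|---|
| 0% | 0 to 2, at most 3 | 7, about 14 |
| 2% | 2, about 5 | 7, about 15 |
| 5% | 3, about 7 | 7 to 8, 15 to 16 |
| 10% | 4 to 5, 9 to 10 | 8, about 16 |

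The readings differ less as the loss rises.

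**5. Power.** For the two smallest arms at 85% retention, pairwise power is 80.0% as planned. With a random slot and no loss it is 79.1% at the median and 77.8% at the 5th percentile of lists, so the fall there is 80.0 − 77.8 = 2.2 points. With a rotated slot or length 12 it is at least 79.7%.

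The three-arm test that precedes the pairwise tests can be approximated by a one-way F-test at Week 6. As planned, its power is 83.3% if one arm differs from the other two by 0.50, and 70.8% if the arms are evenly spaced with 0.50 between the extremes. With a random slot the 5th percentiles are 81.6% and 68.9%, falls of about 1.8 and 1.9 points.

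**The case against.** The strongest reply is that this is a slip of wording. The 4 may mean four per arm, or the programmer may have rotated the doubled arm; either fits 1:1:1 and leaves the arms almost equal. That stands as far as it goes. A reader might infer from the sentence that the randomisation list itself is faulty, but the documents do not show that. They show a sentence that fits 1:1:1 only under a rule it does not give.

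A reader might also infer that the block size alone prevents the list from being regenerated. It does not: section IV gives no seed, so the list could not be regenerated from the protocol even with a valid block length. Nor is blocking the only detail left open, since section IV is also silent on any stratification of the list and on concealment of later rows. What survives is narrower: the stated structure conflicts with the stated ratio.

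Finally, the consequence is small. The repeated-measures model in section VI does not need equal arms. The gap of about 7 belongs to one reading only, and early loss erodes the advantage of the others. All of this is accepted, and it is why the point is rated minor. It does not remove the conflict in the sentence.

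**Conclusion.** Wrong as written; minor. A balanced permuted block for three equal arms cannot have length 4, and no other part of the document resolves the conflict.

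The effect is confined to the balance that blocking guarantees. The typical gap between arms ranges from 0 to 2 participants (rotated slot or length 12, no early loss) to about 7 (random slot). The loss rates used to extend this are assumptions.

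A reader might infer a serious loss of power. The only reading that would produce one doubles the same arm in every block: the two smaller arms of 56 would retain about 47 each (56 × 0.85 = 47.6), with pairwise power near 67%. The document's own ratio and its 75 per group rule that out. Under the remaining readings, pairwise and three-arm power fall by about 2 points or less at the 5th percentile of lists; only rarer random-slot lists lose more. These figures assume two-sided alpha 0.05, d = 0.50 and 85% retention. The sample size of 225 stands.

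**What to change.** Check the PROC PLAN code and the list it produced. The document does not say whether randomisation has begun, so the change depends on that.

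- **If it has begun:** keep the list. Correct the sentence in section IV to the block length or lengths and composition actually used, say how they give 1:1:1, and report the achieved arm sizes.
- **If it has not:** replace the block size of 4 with a small stated multiple of 3, for example 3, 6 or 9, or a random mix of these, and generate the list to match. The length should be kept small because a block of length 3k, stopped at any row, can leave a gap of up to k. Include enough rows for people randomised but never onboarded: on average 225/0.95 ≈ 237 rows at an assumed 5% loss, or 225/0.90 = 250 at 10%, plus a margin.

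The cost is one protocol sentence and, only if randomisation has not started, a new list. No additional participants are needed.

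### No allocation concealment is described: in an unblinded trial of the team's own app, study staff take consent and read the arm from a pre-generated sheet, so the next assignment could be foreseen

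*Combined protocol and SAP*

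**What the plan says.** Section IV (Subject Enrollment) of the combined protocol and SAP gives the whole procedure.

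- **Sequence.** "Randomization will occur via a randomization sheet, as generated using the PROC PLAN procedure in the statistical software package SAS". The ratio is 1:1:1 across SiS, QG and TAU, with a fixed block size of 4.
- **Consent.** On the enrollment call, "study staff will ask the participant to give verbal consent to enroll in this study". Staff enter the date and time of that consent in REDCap.
- **Assignment.** "After providing verbal consent, the participant is randomized", and then "Study staff will use the randomization sheet to determine the" participant's group, which they record in REDCap. Staff go on to onboard the participant to the assigned materials.
- **Blinding.** "This is an unblinded study".
- **Timing of the call.** The participant names a quit date and the call is set 8 days earlier. If that lands on a weekend, "the enrollment call will be adjusted to fall on a weekday".
- **Discretion at screening.** A "participant is screened out unless there is a compelling reason to justify missed check items". That exception requires review with the principal investigator and a phone conversation with the participant.

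No section says who holds the sheet, whether upcoming rows are covered, whether the block size is withheld from enrolling staff, or whether assignments come from a central or independent source. For assignment, REDCap's stated role is to record the result.

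**The concern.** Randomisation protects a group comparison only if nobody who influences enrolment can know the next assignment. A list generated in advance shows every future row to whoever can open it. Taking consent before randomising governs when a row is used, not when it can be seen.

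Three features make this matter here. The team developed SiS (Section I, part 4). The primary outcome, the SEQ, is self-reported. And the Aim 1 model in Section VI treats baseline as one level of TIME and tests the group contrast at Week 6, so a baseline imbalance created by selective enrolment would not be adjusted out of that contrast.

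The two levers the text leaves open are how the consent conversation is conducted and the order in which calls falling on the same day are made. If either is used with knowledge of the next row, even without intent, the arms may differ before treatment begins.

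**Working it through.** **The plan's own figure.** Section VI powers for d = 0.50. Power and sidedness are not stated; I assume 80% and two-sided 5%. The two-sample t-test then needs 63.77, rounded up to the plan's 64 per group. 64/0.85 = 75.3, against the plan's 75 (75 × 0.85 = 63.75), and 3 × 75 = 225. This reproduces within rounding, and concealment does not change it.

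**How predictable the next assignment could be.**
- By chance, with three equal arms: 33.3%.
- With an open sheet: 100%.
- With a hidden sheet, a known fixed block of 3 and visible past assignments: the best guess is right with probability 1/3, then 1/2, then 1, which averages 61.1%. One assignment in three is certain.
- With a known fixed block of 6: 56.1% on average, and 20.0% certain.
- With a block of 4: three equal arms would need 4/3 of a participant per arm, so the stated ratio and block size cannot both hold within a block.

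Hiding the sheet alone therefore leaves some predictability in an unblinded trial.

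**Size of the possible bias.** The documents give no steering figure, so these inputs are assumptions. Suppose 10% of SiS places go to people 0.5 SD higher on self-efficacy and 10% of TAU places to people 0.5 SD lower, with QG unaffected and the difference persisting to Week 6. The arm means shift by +0.05, 0 and -0.05 SD, a SiS-TAU bias of 2 × 0.10 × 0.5 = 0.10 SD, one fifth of the design effect of 0.50.

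- *Ungated SiS versus TAU.* SE = sqrt(2/64) = 0.177 SD. Shift = 0.10/0.177 = 0.566 SE. P(|Z + 0.566| > 1.96) = 8.7%.
- *Three-group contrast.* Noncentrality = 64 × (0.05² + 0² + 0.05²) = 0.32. A chi-square on 2 df then rejects with probability 7.5% instead of 5%.
- *Gated SiS versus TAU.* Section VI runs pairwise tests only if the three-group contrast gives p < 0.05. I simulated three independent arm means with known variance and counted a pairwise rejection only when the three-group test also rejected. Runs of 400,000 and 2,000,000 trials gave 4.9% and 4.8%, against 2.5% with no steering.
- *Gated SiS versus QG.* The bias here is only 0.05 SD, and the gated rate is 3.3% (5.9% ungated).

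Range, with no true effect and the SiS and TAU shifts equal and opposite:

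| Assumed SiS-TAU bias at Week 6 | Three-group test | SiS vs TAU, gated | SiS vs TAU, ungated |
|---|---|---|---|
| 0 | 5.0% | 2.5% | 5.0% |
| 0.05 SD | 5.6% | 3.1% | 5.9% |
| 0.10 SD | 7.5% | 4.8-4.9% | 8.7% |
| 0.15 SD | 10.8% | 8.0% | 13.6% |

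If a 0.10 SD baseline imbalance carries forward with an assumed baseline to Week 6 correlation of 0.5, it becomes 0.05 SD and the second row applies.

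**The case against.** A reader might infer that allocation is known to be open, that staff choose whom to call with baseline SEQ scores in view, and that both SiS comparisons are therefore biased. The documents do not support that.

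- Section IV does not say that the person on the call can see the sheet before consent, or that one person performs every task. It says the sheet is used after consent.
- The baseline survey is part of screening and contains the SEQ (Section V, Table 1), and responses are reviewed before enrolment. The stated review concerns completeness and check items. Nothing says enrolling staff look at SEQ scores.
- The call date follows the participant's quit date, with only a weekend shift, so scheduling is a weak lever.
- The check-item waiver needs the principal investigator and comes before the quit date is chosen. Which row that person will receive depends on who else enrols in between.
- A time record of consent already exists in REDCap.
- The plan's three-group gate roughly halves the pairwise error rates. In the 0.10 SD scenario neither SiS comparison exceeds 5% after the gate.
- If selection were on measured baseline SEQ, a baseline covariate could remove much of the bias.

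All of this stands, and it limits the claim. It does not supply the missing safeguard. The consent record does not hide future rows, the baseline covariate is not planned, and it would not capture selection on a staff member's impression of the caller. The gate lowers the pairwise rates, but the three-group test itself still exceeds its nominal 5%.

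**Conclusion.** The point holds as a defect in the stated procedure. Study staff consent, assign from a pre-generated sheet and onboard, in an unblinded trial of the team's own app, and no concealment is described. The text permits foreknowledge and selective enrolment; it is not evidence that either occurs.

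The size is unknown. At an assumed 0.10 SD SiS-TAU bias at Week 6, with 64 per arm and no true effect, the three-group false-positive rate is about 7.5% instead of 5%, and the gated SiS versus TAU rate is just under 5% instead of 2.5%. The 8.7% figure applies only to an ungated SiS versus TAU test and should not be read as the error rate of the plan or of SiS versus QG. Every steering input is assumed. The case for change rests on the absent safeguard and how cheaply it can be added, not on any one of these rates.

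**What to change.** Amend Section IV as follows.

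1. Someone with no part in enrolment generates and holds the list. Enrolling staff cannot view it.
2. Each arm is released one at a time through a central function, such as one in REDCap, which is already in use, or an equivalent. Release happens only after eligibility, any check-item waiver and the time-stamped verbal consent have been saved.
3. Replace the block size of 4 with varying block sizes that are multiples of 3 and are not disclosed to enrolling staff.
4. If enrolment has begun, record who held the sheet and who could view it, so that readers can judge the risk for participants already assigned.

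The cost is a short set-up and a protocol amendment. No participants or visits are added, and N stays 225.
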